
SA4: As an exploratory aim, assess the demographics and potential barriers to treatment for a third comparator of the “no show” group who were placed in Telehealth, OCIC or inpatient treatment but never showed up or left the inpatient unit against medical advice (AMA). Please see section 6.2 Treatment Compliance to view plan regarding follow up for this “no show” group.
 
SA5: As an exploratory aim, assess the impact of the COVID-19 pandemic on social and emotional functioning.
	
 • The no show group (the third comparator) who did not arrive for any OCIC appointments or left AMA from inpatient treatment will differ from the other comparators with respect to the following barriers to treatment: 1) Age 2) Gender ⁵³⁻⁵⁶ 3) Type of Insurance (public insurance/no insurance/private) ⁶¹⁻⁶³ 4) Ethnicity (Hispanic/Non) ⁶⁴; 5) Race (African-American (AA) versus non-African American) ⁶⁵⁻⁶⁷; 6) Living with one biological parent, two biological parents, a stepparent, a relative, or other ^{68, 69} • The no show group will have significantly shorter time to first recurrence of a suicidal event and a larger number of suicidal events over 90 days and 180 days in comparison to the other patients. • We hypothesize that the levels of perceived stress and depressed mood have been increased amidst the COVID-19 pandemic.

4. Study Design

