9.1. Sample Size Determination

We proposed to recruit approximately 244 eligible cases that will be followed in three treatment arms: telehealth CIS, in-person OCIC, and inpatient. We expect that the sample sizes for the three arms will be *at least* 75, 75, and 70 respectively. These numbers account for an expected 10 % dropout rate; 220 participants are expected to complete study procedures. Prior evidence suggests that the 6-month inpatient readmission rate for adolescents with a prior history of suicidality is approximately 19%.¹⁰⁸ Preliminary data suggest that almost 10% of adolescents who received OCIC treatment following a suicidal event could have recurrent suicidal attempts during the following 6 months after OCIC treatment (preliminary unpublished data from the sites from Dallas and Cincinnati). Therefore, if we assume the hazard ratio (inpatient group vs. OCIC group) will be approximately 2.8 and the readmission rates over 6 months for the two groups will be 19% (for the inpatient group) vs. 10% (for the OCIC group), we will be able to achieve the statistical power at 0.70 given the two-side alpha value = 0.05. We expect numbers for the

Telehealth CIS to be larger than the inpatient group. We will achieve similar power when we compare the Telehealth CIS group with the inpatient group. The power is likely lower than 0.6 when we compare Telehealth CIS with the OCIC group since the effect size (i.e., hazard ratio < 2). The power calculation, based on the assumption that 19% (inpatient group) vs. 10% (Telehealth CIS or OCIC group) will be the averaged recurrence rates for the two arms across the four sites, was performed using the powerSurvEpi package in the software R. For continuous outcomes, we expect that the two-group comparison can achieve the power at 0.84 when the effect size Cohen's d is 0.5 and sample sizes for the first and second group are 75 and 70, respectively. Alternatively, we will achieve the power at 0.76 if we use ANOVA to evaluate whether the continuous outcome differs among the three groups given the effect size $f^2 = 0.2$

For purposes of analysis, the following populations are defined:

Population	Description
Enrolled	All participants who sign the ICF
Observational	All patients will be followed in three treatment arms (telehealth CIS, in-person OCIC, and inpatient)

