Evaluatable	Inclusion: 1) Adolescents (12 to 18 years old) who were brought to the ED due to suicidal thoughts or behaviors and require a higher level of care (Telehealth, OCIC or inpatient); 2) The presence of a legal guardian. Exclusion: 1) Adolescents with suicidal thoughts who had prior OCIC treatment in the past 12 months will be excluded; 2) Adolescents without the ability to answer survey questions will be excluded.
Safety	Participants will be analyzed according to the treatment they actually received.

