9.2.1. Efficacy Analyses

Endpoint	Statistical Analysis Methods
Primary	The primary outcome measure for this proposed research will be the time to first recurrence of a suicidal event. We will examine if the treatment option can predict the “time to the first suicidal event” using the Cox-proportional hazard model.
Secondary	The secondary outcome is Satisfaction with Life (SL), which will be measured every two weeks. The treatment effect on such time-series

	data will then be analyzed using mixed-effect ordinary logistic regression model.
Exploratory	Will be described in the statistical analysis plan finalized before database lock

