9.2.2. Safety Analyses

All safety analyses will be performed on the Safety Sample.

Endpoint	Statistical Analysis Methods
Primary	Our primary outcomes are direct measures related to safety. Our treatments will not be associated with any safety concerns other than the primary outcome that will be analyzed in the treatment efficacy research.
Exploratory	Will be described in the statistical analysis plan finalized before database lock

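### The primary Cox model has no named analysis population, and the only rule for classifying arms is treatment actually received, with no time limit

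*Combined protocol and SAP*

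**What the plan says.** Section 9.2.1 gives the primary analysis in one line: "We will examine if the treatment option can predict the" time to the first suicidal event, using a Cox model. It names no population. Sections 4.2 and 9.2.3 repeat the model for Aim 1 and also name none.

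Section 9.1 defines four populations. The Observational one covers all patients followed in the three arms but is tied to no analysis. The Safety one alone says how patients are classified: "Participants will be analyzed according to the treatment they actually received".

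Section 9.2.2 then says "All safety analyses will be performed on the Safety Sample" and "Our primary outcomes are direct measures related to safety". The same section adds that there are no safety concerns "other than the primary outcome that will be analyzed in the treatment efficacy research". Section 9.2 leaves the selection of analysed participants to a later SAP.

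In section 3, exploratory aim SA4 makes a separate comparator of patients who were placed in a setting but never attended, or who left inpatient care against medical advice (AMA). It predicts: "The no show group will have significantly shorter time to first recurrence of a suicidal event". Section 6.2 keeps non-attenders and refusers in follow-up until they withdraw.

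Eligibility is described in two ways. Section 4.1 ties it to receiving treatment in one of the arms. Sections 5.1 and 6.1 tie it to the clinician's decision on setting.

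**The concern.** SA1 asks how safe telehealth is relative to the other two settings. Attendance, refusal, leaving AMA and later admission all happen after the setting is chosen, and the plan itself expects non-attenders to do worse on the primary outcome. Defining arms by what was received therefore conditions on a post-assignment variable linked to outcome.

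There are two routes to bias. First, a patient who never attends has received none of the three treatments, so the as-received rule gives that patient no arm. Second, section 6 expects the first telehealth contact within 7 business days of the crisis assessment, section 8.2.2 says outpatients who worsen may be admitted, and section 2.2 counts hospitalization for suicidal risk as a primary event. With no time rule, a patient admitted before the first outpatient visit could be counted as inpatient, and the event would go along.

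If the plan is instead read as leaving the population open, the choice between as-assigned and as-received could be made after outcomes are seen.

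**Working it through.** **1. The plan's own figure.** The documents give no number on this point. The nearest is the power of 0.70 in section 9.1 (hazard ratio 2.8, 6-month rates 19% and 10%, two-sided alpha 0.05), which shows how few events there are. By Schoenfeld's formula, power = Φ(√(d·π₁·π₂)·ln HR − 1.96).
- With 244/3 ≈ 81.3 per arm, d = 81.3×0.19 + 81.3×0.10 = 23.6 and power is 0.705. The stated figure reproduces.
- With the stated 70 inpatients and 75 outpatients, d = 13.3 + 7.5 = 20.8 and power is 0.65.

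About 21 to 24 events per comparison leaves little room for moving patients between arms.

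**2. Removing no-shows.** Assumptions, not in the documents: a fraction q of an arm are no-shows with h times the hazard of attenders. The as-assigned 6-month risk p is the same in both arms, so the true hazard ratio is 1.00. Values of p are 10% and 19% (section 9.1) and 27.3% (the 6-month event rate at one site, section 2.2). Attender survival S solves (1−q)S + qS^h = 1−p. The ratio after removal is ln S_A / ln S_B, where A is the arm with more no-shows.

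Example with p = 0.19, h = 2, q = 20% against 5%:
- Arm A: 0.2S² + 0.8S = 0.81 gives S = 0.837.
- Arm B: 0.05S² + 0.95S = 0.81 gives S = 0.817.
- Ratio: 0.1776/0.2016 = 0.88.

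Ranges below are over the three values of p.

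| No-shows, A / B | h = 1.5 | h = 2 | h = 3 |
|---|---|---|---|
| 10% / 10% | 1.00 | 1.00 | 1.00 |
| 10% / 0% | 0.95–0.96 | 0.91–0.92 | 0.84–0.86 |
| 20% / 5% | 0.93–0.94 | 0.88 | 0.79–0.81 |
| 20% / 0% | 0.91 | 0.84–0.85 | 0.73–0.75 |
| 30% / 5% | 0.89–0.90 | 0.81–0.82 | 0.69–0.71 |

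**3. The same question from the other side.** Suppose attenders have equal risk in both arms (10% or 19%). The as-received ratio is then 1.00. With no-shows kept in their arm, and h from 1.5 to 3, it is 1.05–1.18 (10%/0%), 1.07–1.25 (20%/5%) or 1.12–1.43 (30%/5%). The as-received analysis would hide that difference.

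**4. Relabelling an early admission.** Assume 10% risk in both arms: 7.5 events in 75 telehealth patients and 7 in 70 inpatients, ratio 1.00. Move two telehealth-assigned patients whose event was an admission before the first visit. Telehealth becomes 5.5/73 and inpatient 9/72. The ratio is ln(1−5.5/73)/ln(1−9/72) = 0.0783/0.1335 = 0.59. Moving one gives ln(1−6.5/74)/ln(1−8/71) = 0.0919/0.1195 = 0.77. This route does not need unequal no-show rates. The number of such patients is unknown.

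**The case against.** A reader might infer that the plan commits the primary Cox model to an as-treated set, takes no-shows out of their arms, and so makes telehealth and OCIC look safer than they are. The documents do not support that chain.

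- **Population.** Section 9.2.2 also sends the primary outcome to the efficacy analysis, where none is named. Section 9.1 has an all-patient population, and section 9.2 defers selection to the SAP. The as-treated reading is available but not fixed.
- **Removal.** SA4 is exploratory. No text takes no-shows out of the Aim 1 model, and section 6.2 keeps following them.
- **AMA patients.** They did receive inpatient care, so the as-received rule alone keeps them in that arm. Only the SA4 grouping would move them, and it would take poor-prognosis patients out of inpatient, which works against the supposed direction.
- **Direction.** The documents give no no-show rate for any setting, and no reason why telehealth and OCIC should differ.
- **Relabelling.** It is possible under the text but not prescribed.
- **Estimand.** Clinicians choose the setting, so an as-assigned analysis lacks the protection of randomisation, and the effect of care received is a legitimate question.

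All of this stands, and it rules out a claim of known bias. It does not supply the missing population, the missing time rule or a way to classify a patient who received nothing.

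**Conclusion.** The concern holds as a specification defect with a conditional bias. The primary analysis population is not named, the one stated classification rule depends on behaviour after assignment, and that rule has no time limit. If the primary comparison is run as received, it can be biased.

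Size and direction cannot be derived from the documents. Equal no-show rates and equal excess risk in otherwise alike arms give no bias from removal. Under the assumed differences of 10 to 25 points in no-show rate and 1.5 to 3 times the hazard, a true hazard ratio of 1.00 moves to about 0.69 to 0.96, favouring whichever arm has more no-shows. With some 21 to 24 events per comparison, relabelling even one or two early admissions could matter as much, but that too rests on an assumed count.

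**What to change.** - State in sections 9.1 and 9.2.1 that the primary Cox model classifies patients by the setting assigned by the clinician at the crisis assessment, with time counted from that date.
- Keep no-show and AMA patients in their assigned arm. A later admission for suicidal risk is an event in that arm, not a change of arm.
- Report no-show and AMA rates by arm.
- Keep the as-received analysis as a sensitivity analysis, with a stated time window for what counts as received. Keep SA4 as a descriptive comparison whose members also stay in the Aim 1 arms.
- Reconcile the eligibility wording in section 4.1 (receipt of treatment) with SA4, 5.1, 6.1 and 6.2. Taken literally, 4.1 would leave SA4 without patients who never attended.
- Where consent comes after assignment, say in the SAP how the days before consent are handled.

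The cost is wording in the protocol and SAP. Assignment is known before enrolment (section 6.1), and non-attenders are already followed (section 6.2). The downside is that the estimate describes being sent to a setting rather than attending it, and this estimand should be stated. Adjustment for confounding is still needed because clinicians choose the setting.

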9.2. Statistical Analyses

The statistical analysis plan will be developed and finalized before database lock and will describe the selection of participants to be included in the analyses, and procedures for accounting for missing, unused, and spurious data. Below is a summary of planned statistical analyses of the primary and secondary endpoints.

9.2.1. Efficacy Analyses

Endpoint	Statistical Analysis Methods
Primary	The primary outcome measure for this proposed research will be the time to first recurrence of a suicidal event. We will examine if the treatment option can predict the “time to the first suicidal event” using the Cox-proportional hazard model.
Secondary	The secondary outcome is Satisfaction with Life (SL), which will be measured every two weeks. The treatment effect on such time-series

	data will then be analyzed using mixed-effect ordinary logistic regression model.
Exploratory	Will be described in the statistical analysis plan finalized before database lock

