
 Evaluate the safety of CIS-telehealth relative to inpatient and OCIC-in-person among children with similar CHRT scores. 	
 Time to first recurrence of a suicidal event Number of suicidal events Severity of suicidal ideation
Secondary	

 Examine the effectiveness of CIS-telehealth relative to inpatient and in-person OCIC among children with similar CHRT scores. 	
 Score from PROMIS Short Form v 1.0-General Life Satisfaction-Short Form 5a (to assess the parent's well-being) Score from PROMIS Parent-Proxy Life Satisfaction-Short Form 8a Score from PROMIS Pediatric Life Satisfaction-Short Form 4a Score from CHRT-SR at baseline and follow-up visits

 Assess patient and parent treatment satisfaction with CIS-telehealth relative to inpatient and in-person OCIC among children with similar CHRT scores. 	
 Score from Client Satisfaction Questionnaire (CSQ-8)
Tertiary/Exploratory	

 Does Telehealth CIS lead to greater reduction of emotional arousal or perceived stress levels in response to COVID-19 the pandemic 	
 Scores from the COVID-19 survey

CONFIDENTIAL

Overall Design: Observational Design

Number of Participants: CCHMC- 61; other 3 sites- 61 each; total- 244 from all 4 sites

Treatment Groups: Inpatient Psychiatric Treatment vs. Outpatient Crisis Intervention Clinic (OCIC) vs. Telehealth Crisis Intervention Services (CIS)

Duration: 12 Months (1 Years)

2. Introduction

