8.1. Efficacy Assessments

- Time to first recurrence of a suicidal event and number of suicidal events will be measured with the Suicidal Event Form for START (appendix), a short supplemental form (developed by our team), at baseline and every two weeks (see Schedule of Events; appendix)
- Severity of suicidal ideation will be measured with the self-report scale: CHRT-SR and C-SSRS (appendix) at baseline and every two weeks (see Schedule of Events; appendix).
- The Suicidal Treatment AlteRnatives for Teens (START)-Clinical Features (CF) form (appendix), a short supplemental form with 13 questions (developed by our team), will be completed at baseline (within 72 hours of admission to inpatient, telehealth CIS, or OCIC) and every two weeks to monitor substance use based on information from patient, parent, and/or EHR.
- Satisfaction with Life (SL) will be measured with self-report scales including the PROMIS Short Form v 1.0-General Life Satisfaction-Short Form 5a (to assess the parent's well-being), PROMIS Parent-Proxy Life Satisfaction-Short Form 8a, and PROMIS Pediatric Life Satisfaction-Short Form 4a every 2 weeks.

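### Section 9.2.1 assigns the Satisfaction with Life scores to a logistic mixed model but defines no cut-off or ordered categories for them

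*Combined protocol and SAP*

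**What the plan says.** Section 9.2.1 (Efficacy Analyses, Secondary row) reads "The secondary outcome is Satisfaction with Life (SL), which will be measured every two weeks", and says that these "data will then be analyzed using mixed-effect ordinary logistic regression model". No other model is given for this outcome.

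The outcome is a score. The synopsis lists among its secondary endpoints "Score from PROMIS Parent-Proxy Life Satisfaction-Short Form 8a" and "Score from PROMIS Pediatric Life Satisfaction-Short Form 4a", together with the 5a form for the parent. Section 8.1 agrees: "Satisfaction with Life (SL) will be measured with self-report scales including the PROMIS Short Form v 1.0-General Life Satisfaction-Short Form 5a" and the other two forms. The Schedule of Events collects all three at baseline and at weeks 2 to 22, which makes 11 follow-up visits. No section defines a responder, a threshold or a grouping of these scores.

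Section 9.1 bases the power for outcomes of this type on means: "For continuous outcomes, we expect that the two-group comparison can achieve the power at 0.84", where Cohen's "d is 0.5 and sample sizes for the first and second group are 75 and 70, respectively". It also gives an ANOVA figure. It gives no power for a binary or ordinal outcome, and it does not name Satisfaction with Life.

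**The concern.** Ordinary logistic regression, with or without random effects, takes a two-level outcome. A multi-item score is not one, so the sentence cannot be carried out without a decision that the plan does not make: where to cut each of three scores. If that decision is made after outcome data exist, the result can depend on the choice. Any cut also discards the differences among participants on the same side of it.

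The estimate changes as well. A logistic model yields an odds ratio, whereas the effect size in 9.1 for continuous outcomes is a standardised mean difference.

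**Working it through.** **Inputs.** From 9.1: d = 0.5, groups of 75 and 70, stated power 0.84. Two-sided alpha of 0.05 is stated there for the survival calculation and assumed to apply here. From the Schedule of Events: 11 follow-up visits. Assumed, because the document gives no value: normally distributed scores, the cut-offs, and the correlation between visits.

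**1. The plan's own figure.** The standard error of the standardised difference is √(1/75 + 1/70) = 0.1662, and 0.5/0.1662 = 3.009. Normal approximation: Φ(3.009 − 1.960) = 0.853. The noncentral t gives 0.848. The stated 0.84 reproduces as a comparison of means.

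**2. One visit, score split in two.** Place the group means 0.25 SD either side of the centre and cut at the centre. The proportions above the cut are 0.401 and 0.599, difference 0.197. With the pooled standard error 0.0831 under the null and 0.0815 under the alternative, power = Φ((0.197 − 1.960 × 0.0831)/0.0815) = 0.664. This was the highest power among the cuts tried. Cuts 0.5 and 1 SD from the centre give 0.62 and 0.50. At the central cut, about 111 per group would be needed to reach 0.84.

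**3. Eleven visits, sustained effect.** Section 9.2.1 specifies a repeated-measures model, so step 2 alone does not describe it. Approximate the model by comparing each participant's average over the 11 visits, with d = 0.5 at every visit, equal correlation ρ between visits and no missing data. For the score, the variance of the average is (1 + 10ρ)/11. At ρ = 0.8 that is 0.818, so 0.5/√(0.818 × 0.0276) = 3.326 and power = Φ(3.326 − 1.960) = 0.914. For the central split, ρ = 0.8 on the score becomes 0.587 on the two-level variable. The variance of the averaged proportion is 0.240 × (1 + 10 × 0.587)/11 = 0.150, so 0.197/√(0.150 × 0.0276) = 3.07 and power = 0.866.

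| Assumed ρ | Score | Central cut | Cut 0.5 SD above centre | Cut 1 SD above centre |
|---|---|---|---|---|
| 0.5 | 0.983 | 0.972 | 0.961 | 0.915 |
| 0.7 | 0.942 | 0.911 | 0.887 | 0.799 |
| 0.8 | 0.914 | 0.866 | 0.834 | 0.729 |

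The loss from splitting is 1 to 5 points at the central cut and 7 to about 19 points at the 1 SD cut.

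**4. If *ordinal* was meant.** The score was grouped into 5 or 10 equal categories and compared by a rank test at one visit (6,000 simulated trials, d = 0.5, 75 against 70). Power was 0.81 and 0.83; the t-test in the same simulations gave 0.85.

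**The case against.** The strongest reply is that *ordinary* is a slip for *ordinal*. Section 9.2.3, in the COVID-19 survey analysis, pairs ordinal logistic regression with ordinal outcomes and a generalized linear model with continuous ones, so the authors know the difference. Section 9.2.1 never mentions a threshold, and a mixed-effect ordinal model is a recognised choice for repeated ordered data. This is probably right. It removes the two-level objection and most of the power loss. It leaves the wording wrong and does not say how multi-item scores become ordered categories. By the pairing in 9.2.3, a scored scale would sit more naturally with the continuous outcomes.

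A second reply is that section 9.2 calls the table a summary and promises a statistical analysis plan before database lock. That plan could settle the categories. But the secondary row commits to a model, and only the exploratory row is deferred.

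A third is that 9.1 speaks of continuous outcomes in general and never names Satisfaction with Life, while the GLM in 4.2 and 9.2.3 concerns emotional arousal and treatment satisfaction. This stands: the link between the 0.84 and this endpoint is an inference. It is a reasonable one, because this is the secondary outcome named in 9.2.1 and it is scored.

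**Conclusion.** The model named in 9.2.1 does not fit the endpoint as the text stands, and the wording needs correcting on either reading. Taken literally, it requires an undefined split. That costs about 19 points of power at a single visit at the central cut (0.85 to 0.66). For a sustained effect over 11 visits it costs about 1 to 5 points at a central cut and up to about 19 at a cut 1 SD away. Read as *ordinal*, the cost is a few points at a single visit. These sizes rest on normal scores, assumed cut-offs and, for repeated visits, assumed correlations of 0.5 to 0.8 with complete data.

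Two stronger readings are not supported. A reader might infer that the model cannot be fitted. It can, once a cut-off or categories are chosen; the fault is that the plan does not choose them. A reader might also infer that the stated 0.84 would be lost. The fall to 0.66 applies to one visit only. Over 11 visits with a sustained effect, a central cut gives 0.87 to 0.97, and 9.1 does not tie the 0.84 to this endpoint in any case.

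**What to change.** Preferred: in 9.2.1, replace the model with a linear mixed model fitted to each PROMIS score, with arm, visit, arm-by-visit and baseline score as fixed effects and a random intercept per participant. Report differences in means between arms with 95% confidence intervals. This agrees with the continuous-outcome basis in 9.1.

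If an ordinal analysis is intended: correct *ordinary* to *ordinal*, state how each score enters as ordered categories, adjust for the baseline score, and say that the 0.84 in 9.1 applies to a comparison of means.

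Either is an edit of a line or a short paragraph, best made before outcome data are examined. The Schedule of Events already collects the scores at baseline and every follow-up visit, so no new data are needed.
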